#### 4.2 Secondary Efficacy Endpoints

The key secondary efficacy endpoints are:

- Change from baseline in log10 viral load, as measured using saliva and as measured using nasal swab. Changes will be calculated as value at follow-up visits – value at baseline.
- Time to sustained clinical resolution of symptoms.

Sustained clinical resolution is defined as occurring when no key COVID-19 related symptom has a score higher than 1 over a 72-hour period (as documented using an electronic patient-reported outcome [ePRO] instrument or in the eCRF), except for sense of smell and taste (items 13 and 14) where the score should be 0 over a 72-hour period. The time to resolution will be taken as the time from randomization until the first day of the last 72-hour period where the patient meets the definition of resolution within 28 days. Patients who do not meet the definition of resolution 28 days after randomization will be considered not resolved.

Refer to the algorithm in Appendix 1 for the derivation of this endpoint.

Other secondary efficacy endpoints are:

- Time to viral clearance based on PCR test for SARS-CoV-2, as measured using saliva and as measured using nasal swab
- Time to complete clinical resolution of symptoms (excluding cough, sense of smell and taste)

Clinical resolution is defined in the same way as the primary endpoint, but considering that all symptoms (excluding cough, sense of smell and taste) must resolve to a score of 0 for 72 hours.

- Time to complete clinical resolution of symptoms

Clinical resolution is defined as occurring when all key COVID-19 related symptom must resolve to a score of 0 for 72 hours.

The derivation of this endpoint follows similar steps as the algorithm presented in Appendix 1.

- Change from baseline in COVID-19 total symptom score

Total symptom score is defined as the sum [range 0-42] of the scores of all 14 common COVID-19 symptoms.

- Score on the WHO Clinical Outcome Scale (9-point scale) [as collected on eCRF Form “WHO COVID-19 Clinical Improvement Score”]
- Rate of hospitalization [hospitalization will be identified in the eCRF Form “Adverse Event” if adverse event is serious and serious category is Hospitalization or prolonged hospitalization]
- Rate of progression to oxygen therapy [progression to oxygen therapy will be identified in the eCRF Form “Adverse Event” if event requires supplemental oxygenation or mechanical ventilation or extracorporeal membrane oxygenation]
- Duration of hospitalization [duration will be identified in the eCRF Form “Adverse Event” as the difference between date of discharge and date of admission]
- Mortality rate [death will be identified in the eCRF Form “Adverse Event” if outcome of adverse event is fatal]

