**Table 3: Assessment of 14 Common COVID-19-Related Symptoms: Items and Response**

Symptom	Response and scoring
1. Stuffy or runny nose	
2. Sore throat	
3. Shortness of breath (difficulty breathing)	
4. Cough	
5. Low energy or tiredness	None = 0 Mild = 1
6. Muscle or body aches	Moderate = 2
7. Headache	Severe = 3
8. Chills or shivering	
9. Feeling hot or feverish	
10. Nausea (feeling like you wanted to throw up)	I did not vomit at all = 0 1–2 times = 1 3–4 times = 2 5 or more times = 3
11. How many times did you have vomiting in the last 24 hours?	

Symptom	Response and scoring
12. How many times did you have diarrhea (loose or watery stools) in the last 24 hours?	I did not have diarrhea at all = 0 1–2 times = 1 3–4 times = 2 5 or more times = 3
13. Rate your sense of smell in the last 24 hours	My sense of smell is THE SAME AS usual = 0 My sense of smell is LESS THAN usual = 1 I have NO sense of smell = 2
14. Rate your sense of taste in the last 24 hours	My sense of taste is THE SAME AS usual = 0 My sense of taste is LESS THAN usual = 1 I have NO sense of taste = 2

Sustained clinical resolution is defined as occurring when no key COVID-19 related symptom has a score higher than 1 over a 72-hour period (as documented using an ePRO instrument), except for sense of smell and taste (items 13 and 14) where the score should be 0 over a 72-hour period. The time to resolution will be taken as the time from randomization until the first day of the last 72-hour period where the patient meets the definition of resolution within 28 days. Patients who do not meet the definition of resolution 28 days after randomization will be considered not resolved.

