### **6.2.2 Handling of Missing Data**

#### **6.2.2.1 Imputation**

Severity Symptom Score: Missing values on severity symptom score will not be imputed. However, where a patient has died, their symptom score will not be considered missing, but will be imputed with the maximum severity score (3) for each symptom at each time point.

Clinical Outcome Scale: Missing values on clinical outcome scale will not be imputed. However, where a patient has died, their clinical outcome scale will not be considered missing, but will be imputed with maximum clinical outcome scale (7 [maximum severity if alive] or 8 [maximum severity if dead]) at each time point.

Viral load: Prior to the log 10 transformation, non-numeric viral load results reported as below the limit of detection will be replaced by the limit of detection divided by 2. As an example, results reported as “<2228cp/mL SARS-CoV2 detected” will be replaced by 1114 cp/mL. Non-numeric viral load results reported as “No SARS-CoV2 detected” will be replaced by 1 cp/mL. Replacing by 1 (instead of by zero) will be done so that the log 10 of viral load will be defined in all subjects (and equal to zero when no SARS-CoV2 is detected).

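### The total symptom score runs 0–40, not 0–42; the SAP's death rule goes off the scale for smell and taste and has no date-of-death limit

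*SAP*

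**What the plan says.** SAP section 4.2 defines the endpoint: "Total symptom score is defined as the sum [range 0-42] of the scores of all 14 common COVID-19 symptoms". The SAP has no scoring table of its own. Its resolution definition in the same section refers to smell and taste by the protocol's item numbers ("except for sense of smell and taste (items 13 and 14) where the score should be 0 over a 72-hour period"), so the scoring is that of Protocol Table 3. There the severity-rated and count-rated items end at 3 (for the counts, "5 or more times = 3"), while the last two items end one step lower: "I have NO sense of smell = 2" and "I have NO sense of taste = 2".

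SAP section 6.2.2.1 leaves missing symptom scores and missing WHO scores unimputed, with an exception for patients who died. Their symptom score "will be imputed with the maximum severity score (3) for each symptom at each time point". Their WHO score is "imputed with maximum clinical outcome scale (7 [maximum severity if alive] or 8 [maximum severity if dead]) at each time point". Protocol section 8.8.1 has the same exception but gives no numeric values, so the 3, the 7 and the 8 come from the SAP. Its revision history lists the 7 and 8 as a correction made in Amendment 1.

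**The concern.** There are two separate problems.

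- **Value.** The stated maximum does not follow from the item scores, and the death rule uses the same wrong maximum. A programmer who follows the SAP exactly would create out-of-range data for items 13 and 14. Those data would enter the repeated-measures model for change in total symptom score (SAP section 6.4.3.4).
- **Scope.** Neither death rule says from which visit it applies. Depending on how it is read, the same patient could contribute a large worsening or no change at all. Two programmers could produce different datasets from the same text.

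**Working it through.** **Inputs**

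- Items 1–12: maximum 3 each (Protocol Table 3). The layout around item 10 is unclear, but both candidate response sets end at 3, so this does not matter.
- Items 13 and 14: maximum 2 each (Protocol Table 3).
- Planned arm size 52, so 104 in the two highest doses combined (Protocol section 3.1; SAP section 2.1).

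**1. Reproducing the SAP's maximum.** 14 × 3 = 42. This matches the SAP only if smell and taste could each score 3.

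**2. Maximum under Table 3.** 12 × 3 + 2 × 2 = 36 + 4 = 40.

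**3. Death imputation under the SAP.** 3 on each of 14 items = 42. Excess over the attainable maximum: 42 − 40 = 2 points, 1 on each of items 13 and 14.

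**4. Effect of the excess on a visit mean, per death**, with all planned patients contributing:

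- one arm: 2/52 = 0.04 points
- two highest doses combined: 2/104 = 0.02 points

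**5. Effect on resolution endpoints.** None. The primary endpoint excludes smell and taste. Where those items count, they must be 0, so 2 and 3 both mean not resolved.

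**6. Scope of the death rule.** The WHO rule covers patients who died and assigns 7 if alive or 8 if dead. In Protocol Table 4, 8 is death and 7 is the worst living state. For a patient who has died, a value that depends on being alive can only belong to a visit before the death. The rule therefore reaches back before death to some extent, and no date limits how far. Three readings follow:

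- *Post-death visits only:* the 7 would never be used.
- *All visits without data:* visits missed while alive would be set to the worst values, although the general rule leaves missing values unimputed.
- *Every visit, literally:* observed records, including baseline, would be replaced.

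**7. What the scope does to change from baseline.** The documents give no typical baseline total; 6 to 20 is assumed here for illustration.

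| Reading | Change at an imputed visit |
|---|---|
| Post-death visits, value 42 | 42 − 6 = +36 to 42 − 20 = +22 |
| Post-death visits, value 40 | 40 − 6 = +34 to 40 − 20 = +20 |
| Every visit including baseline, value 42 | 42 − 42 = 0 |

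Under the SAP's value of 42, the post-death and literal readings differ by 22 to 36 points for one patient. On a 52-patient arm mean that is 22/52 = 0.42 to 36/52 = 0.69 points per death, against 0.04 for the off-scale excess.

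**The case against.** The best defence is that little depends on this. The bracketed range is a label: no threshold or rescaling uses it, and observed scores add up correctly whatever it says. Only one of the other secondary endpoints is touched by the off-scale value, and only if someone dies, which should be rare in outpatients with mild to moderate disease. Any pull that a death exerts on the symptom model comes mainly from the decision to give deaths the worst score. That decision is in the protocol and would remain at 40. All of this stands, and it limits the point to a minor correction.

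Two stronger readings are tempting, and the documents do not support them.

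- A reader might infer that impossible or high-leverage values also enter the WHO comparisons. They do not. Scores 7 and 8 both exist in Protocol Table 4, and SAP section 6.4.3.5 compares the groups with a Mann-Whitney-Wilcoxon test, which uses ranks.
- A reader might infer that the SAP orders observed pre-death scores to be overwritten. That is only one reading. The rule sits in the section on missing data and is worded as an exception to leaving missing values alone. An observed ambulatory score is not missing, so a programmer could reasonably leave it untouched.

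The second defence does not dispose of the scope question. Even if only empty visits are filled, the living-patient value of 7 would go to visits missed before death, and the text does not rule out the literal reading.

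The SAP also says that it supersedes the protocol (section 1). That does not rescue 42, because the SAP does not redefine the item scores.

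**Conclusion.** The stated range is wrong: the maximum is 40. Imputing 3 for smell and taste is off the scale by 2 points in total. Both statements are certain under Protocol Table 3, the only scoring in the documents. The resulting bias is negligible, about 0.04 points on a 52-patient arm mean per death and zero without deaths. It is still an error in a rule that will be programmed, and not only in a label.

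The missing date-of-death limit is also real, but it is a gap in specification. The text supports at least the filling of visits missed while alive and leaves open the replacement of observed records; that replacement should not be stated as fact. It is potentially the larger effect per death, by an amount that depends on the assumed baseline. The overall severity is low, because it too arises only if patients die.

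**What to change.** Three short edits to the SAP:

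1. Section 4.2: state the range of the total symptom score as 0–40.
2. Section 6.2.2.1, symptom score: for patients who died, impute each item's own maximum (3 for items 1–12, 2 for items 13 and 14), only at visits on or after the date of death.
3. Section 6.2.2.1, WHO scale: for patients who died, impute 8, only at visits on or after the date of death, and remove the value of 7.

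Both death rules should add that observed scores before death are kept and that earlier missing values stay unimputed, as the general rule already provides. The cost is a few lines of text and the matching derivation code; data collection and conduct do not change.

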## **7.2. Safety and Tolerability Assessments**

### **7.2.1. Adverse Events**

Adverse event definitions, assignment of severity and causality, and procedures for reporting SAEs are detailed in [Appendix 1](#).

The condition of each patient will be monitored from the time of providing informed consent to completion of study participation. Patients will be observed for any signs or symptoms and asked about their condition by open questioning, such as “How have you been feeling since you were last asked?” at each patient contact. Patients will also be encouraged to spontaneously report AEs occurring at any other time during the study.

Any AEs and remedial action required will be recorded in the patient’s source data. The nature, time of onset, duration, and severity will be documented, together with an Investigator’s (or designee’s) opinion of the relationship to study drug.

AEs recorded during the course of the study will be followed up, where possible, until resolution or until the unresolved AEs are judged by the Investigator (or designee) to have stabilized. This will be completed at the Investigator’s (or designee’s) discretion.

For any participants who require hospitalization, if possible, study drug should be continued and an effort made to collect study-related data and conduct End of Study procedures. Every attempt should be made for a visit to be scheduled after discharge from the hospital, providing that the visit is within 28 days of initiation of dosing, or to visit the patient in the hospital, where permitted. In lieu of a study visit, study site staff should obtain equivalent data from hospital records. Pertinent information from hospitalization will be collected, including need for

supplemental oxygenation, mechanical ventilation, days of hospitalization and ventilation, and death.

Serious AEs of worsening COVID-19, with the exception of death, will be considered disease progression and will not be collected for the safety database.

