### Reporting of Adverse Events

At each visit the Investigator, or delegate, will determine whether or not any AEs have occurred. Non-leading questions such as "How are you feeling today?" or "Have you had any health concerns since your last visit?" should be used to elicit the patient to report any possible AEs. If any AEs have occurred, they will be recorded in the AE section of the electronic Case Report Form (eCRF) and in the patient's source documents. If known, the diagnosis should be recorded, in preference to listing the individual signs and symptoms.

Adverse event reporting begins from the time of informed consent and ends 30 days after the last dose of study drug.

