#### **6.4.3.8 Duration of Hospitalization**

The duration of hospitalization will be from the date of first hospitalization until date of discharge [(Date of hospitalization – date of discharge) in the eCRF Form “Adverse Event”]. The duration of hospitalization will be the total number of days hospitalized in case of more than one hospitalization.

The duration of hospitalization will be analyzed on the ITT population in subjects who were hospitalized. Duration of hospitalization will be summarized by treatment group using descriptive statistics (N, mean, median, standard deviation, Q1, Q3, minimum, and maximum). An ANOVA model will be performed to analyze the difference between treatment groups. The model will include only the treatment group.

Contrasts under this model will allow for the comparisons across treatment groups. The results will be presented as mean treatment difference with associated 80% CI and p-value.

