### **6.5.2.2 Serious Adverse Events**

Treatment-emergent serious AEs (TESAE) will be summarized. Number and proportion of subjects experiencing a treatment-emergent serious AE will be presented by system organ class and preferred term overall and for each treatment group.

An overall summary of the total number of TESAEs reported, the number and proportion of subjects experiencing at least one TESAE, at least one severe TESAE, at least one TESAE related to the study treatment, at least one TESAE leading to treatment discontinuation, a TESAE leading to death, at least one TESAE requiring supplemental oxygenation, at least one TESAE requiring mechanical ventilation and at least one TESAE requiring ECMO will also be presented.

Treatment-emergent serious AEs (TESAE) related to study treatment will also be summarized. Number and proportion of subjects experiencing a treatment-emergent serious AE related to study treatment will be presented by system organ class and preferred term overall and for each treatment group.

An overall summary of TESAEs related to study treatment that includes the total number of TESAEs related to study treatment reported, the number and proportion of subjects experiencing at least one TESAE related to study treatment, at least one severe TESAE related to study treatment, at least one TESAE related to study treatment leading to treatment discontinuation, a TESAE related to study treatment leading to death, at least one TESAE related to study treatment requiring supplemental oxygenation, at least one TESAE related to study treatment requiring mechanical ventilation and at least one TESAE related to study treatment requiring ECMO will also be presented.

All SAEs will also be listed (Section 7, Listing 9).

A separate listing for deaths will be also provided (Section 7, Listing 10).

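### Hospitalisation, oxygen progression and length of stay are read only from the Adverse Event form, and the plan does not say whether non-fatal worsening of COVID-19 is entered there

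*SAP*

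**What the plan says.** **SAP 4.2 (Secondary Efficacy Endpoints)** names one source, the eCRF Adverse Event form, for three endpoints:

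- Hospitalisation counts "if adverse event is serious and serious category is Hospitalization or prolonged hospitalization".
- Progression to oxygen counts "if event requires supplemental oxygenation or mechanical ventilation or extracorporeal membrane oxygenation". This rule is not limited to serious events.
- Duration is taken "as the difference between date of discharge and date of admission".

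SAP 6.4.3.8 again takes its dates from that form: "The duration of hospitalization will be from the date of first hospitalization until date of discharge". SAP 6.4.3.6 places hospitalisation details in the AE listing (Listing 9).

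**Protocol 7.2.1 (Adverse Events)** states: "Serious AEs of worsening COVID-19, with the exception of death, will be considered disease progression and will not be collected for the safety database". Just before this it says "Pertinent information from hospitalization will be collected, including need for" oxygen, ventilation, days in hospital and death, without naming a form.

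**Protocol 8.4.2.4** plans to report all hospitalised patients with the reason, and excludes no cause. **Protocol Appendix 1** sends AEs to the AE section of the eCRF. **SAP 6.5.2.2** tabulates patients with "at least one TESAE requiring supplemental oxygenation, at least one TESAE requiring mechanical ventilation and at least one TESAE requiring ECMO", and makes no exception for worsening COVID-19.

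**Protocol Appendix 4** also schedules a check of care setting and, in footnote e, records the dates of WHO scale changes between visits through Day 28. SAP 4.2 uses neither for these endpoints.

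**The concern.** In an outpatient COVID-19 trial, admissions for worsening COVID-19, and the oxygen given during them, are the events these endpoints exist to count. The protocol sets that class of event apart from one dataset. The SAP looks for it in one form. Whether the form and the dataset are the same thing is left unsaid, and no passage requires worsening COVID-19 to be entered on the AE form all the same.

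A site that applies Protocol 7.2.1 to the AE form could leave such an admission off it. The hospitalisation table would then omit the patient, Listing 9 would omit the patient too because it is built from the same form, and the WHO-scale table could disagree with both. Recording is blinded, so there is no reason to expect more omissions in one arm than another. The main cost would be lost events.

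**Working it through.** The plan gives no expected rate for these endpoints, so there is no stated figure to reproduce. The check is a comparison of texts, followed by three small calculations.

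**1. The two readings**

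| Endpoint | If Protocol 7.2.1 covers the AE form | If the safety database is separate from the eCRF |
|---|---|---|
| Hospitalisation | COVID-19 admissions lost (must be a serious AE) | No loss |
| Duration | Same admissions lost | No loss |
| Oxygen progression | Cases recorded only as serious AEs lost; oxygen on a non-serious AE kept | No loss |
| Mortality | Unaffected (death is excepted) | Unaffected |

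Under the second reading nothing conflicts. The only open point is whether the SAP 6.5.2.2 tables are meant to include these events.

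**2. Would the WHO-scale analysis show a missed admission?**

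Inputs: the protocol schedules post-treatment scores on Days 3, 5, 10 and 28. SAP 6.4.3.5 adds Day 14, which the protocol does not schedule for this scale. Assumptions: a stay of n nights occupies days s to s + n inclusive, and start days s are spread evenly over Days 2 to 28 (27 start days).

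- 3 nights: starts 2–5, 7–10 and 25–28 touch a scheduled day, 4 + 4 + 4 = 12. Missed: 27 − 12 = 15, and 15/27 = 56%.
- 7 nights: starts 2–10 and 21–28 touch a scheduled day, 9 + 8 = 17. Missed: 27 − 17 = 10, and 10/27 = 37%.
- If unscheduled Day 14 scores exist, starts 11–14 are also covered. Missed: 11/27 = 41% and 6/27 = 22%.
- If all stays start on Days 3–10 (8 start days), 3 nights misses only a Day 6 start, 1/8 = 13%, and 7 nights misses 0/8, with or without Day 14.

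The dated status changes in footnote e would show the stays that fall between visits.

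**3. The Day 28 visit and the 28-day limit**

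SAP 6.4.3.6 and 6.4.3.7 exclude events dated after randomisation + 28. SAP Appendix 2 places the Day 28 visit 25 to 29 days after first dose. Protocol 3.1 plans screening, with randomisation, 24 to 48 hours before dosing, which is 1 to 2 days. The visit therefore falls at 25 + 1 = 26 to 29 + 2 = 31 days after randomisation. An on-time visit (27 days after first dose) falls at + 28 or + 29. An in-hospital record at + 26 to + 28 proves admission within the limit. A later record does not, without an admission date.

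**4. Illustration of size (assumed rates, not in the documents)**

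Assume 2–5% of 208 patients are admitted: 208 × 0.02 = 4.2 and 208 × 0.05 = 10.4. Let c be the share due to COVID-19 (0.8–1.0) and m the share of those left off the AE form. Found = admissions × (1 − c × m).

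- m = 0: 4.2 to 10.4 found.
- m = 0.5: 4.16 × 0.5 = 2.1 to 10.4 × 0.6 = 6.2.
- m = 1: 0 to 10.4 × 0.2 = 2.1.

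Sparse arms are likely in any case. The chance that at least one of four arms of 52 has no event under full capture is 1 − (1 − (1 − q)^52)^4. For q = 5%, 0.95^52 = 0.069, giving 25%. For q = 2%, 0.98^52 = 0.350, giving 82%.

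**The case against.** The strongest reply is that Protocol 7.2.1 speaks of the safety database, not the eCRF. Other passages fit a separate database: Appendix 1 sends AEs to the eCRF, Section 4.4.5 gives SAE follow-up to a separate patient safety group, and SAP 4.2 and 6.5.2.2 expect oxygen, ventilation, ECMO, admission and discharge data on the AE form. Those fields largely match the hospital data that Protocol 7.2.1 says will be collected. The SAP was written from an annotated CRF that is not among these documents. This stands, and it is why the loss is only possible. It does not close the point, because no passage says that worsening COVID-19 must still be entered.

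A reader might infer that the passages conflict on either reading. They do not. If the safety database is separate, entering and tabulating these events breaks no rule.

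A reader might also infer that oxygen progression is as exposed as hospitalisation. It is less so, because its rule is not limited to serious events. The relief is partial: the protocol's WHO table places oxygen under hospitalised states, and an AE requiring hospitalisation is serious by definition.

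The clause in SAP Section 1 that lets the SAP override the protocol does not settle the matter. An analysis rule cannot supply events that were never entered.

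Finally, these are other secondary endpoints, no power statement or decision rule rests on them, and SAP Section 1 moves the emphasis to viral load. That stands, and it limits the severity.

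**Conclusion.** The point holds as an unresolved question of data source with a possible loss of events. If Protocol 7.2.1 is applied to the AE form, hospitalisation and duration lose the COVID-19 admissions that Protocol 8.4.2.4 means to count, and oxygen progression loses those recorded only as serious AEs. If it is not, there is no loss and no conflict.

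The size cannot be computed from the documents. The counts in step 4 rest wholly on assumed rates and run from no loss to near-total loss. The 56% and 37% in step 2 rest on assumed lengths of stay and evenly spread start days. They describe how incomplete the visit-day back-up is, not how many admissions are lost.

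Two further inferences are not supported: that this gap would be the cause of arms without events, which are likely even with full capture, and that it biases the comparison between arms under blinded recording. Severity is low to moderate.

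**What to change.** Before database lock:

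1. **Reconcile Protocol 7.2.1 with SAP 4.2.** State whether non-fatal worsening COVID-19 is entered on the AE form, and whether the SAP 6.5.2.2 tables include it.
2. **Widen the derivations in SAP 4.2, 6.4.3.6 and 6.4.3.7.** Count hospitalisation from the AE form or a dated post-baseline WHO score of 3–7. Count score 3 only when the setting check or admission dates confirm it, because inclusion criterion 5 attaches score 3 to outpatients while Protocol Table 4 defines it as hospitalised. Count oxygen progression from the AE form or a dated post-baseline score of 4–7. Do not count score 8 alone, since a death does not by itself show admission or oxygen use.
3. **Use the setting check to query for dates.** An in-hospital record at a visit dated on or before randomisation + 28 counts as an admission within the window. A later record needs an admission date.
4. **Take duration from recorded admission and discharge dates**, not from visit scores.

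The cost is SAP wording and a small cross-check of AE, WHO-scale and setting records that the trial already collects. No new visit or assessment is needed. The fix does not depend on a new instruction to sites, which may come too late: SAP 6.2.1 places the interim review near the end of treatment of the last patients. If all events are already on the AE form, the cross-check simply confirms it.
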